1. ABBREVIATIONS AND STATISTICS USED IN THIS ARTICLE

Abbreviations	Explanations in details
AE	Adverse Event
ADE	Adverse Device Event
CHG	chlorhexidine gluconate
CI	Confidence Interval
CLABSI	CLABSI infection
CRF	Case Report Form
CRBSI	Catheter-Associated Bloodstream Infection
CVC	Central venous catheter
DD	Device Defect
DVC	Deep venous catheterization
FAS	Full Analysis Set
ITT	Intention to Treat
Max	Maximum
Mean	Means
Min	Minimum
PICCO	Pulse indicate Contour Cardiac Output
SAE	Serious Adverse Event
SADE	Serious Adverse Device Event
SAP	Statistical Analysis Plan
SAR	Statistical Analysis Report
SD	Standard Deviation
SE	Standard Error
SOC	System Organ Class
SOP	Standard Operation Procedure
SS	Safety Set
USADE	Unexpected Serious Adverse Device Event

2. OBJECTIVES OF THE STUDY

2.1 Primary objective

The primary objective of this study is to compare the difference in the bacterial colonization rate at CVC tips and catheter sites on the skin after removal (number of culture-positive cases/total catheters × 100%) between the test and control groups.

2.2 Secondary objective

The secondary objective of this study is to compare the differences in the following indicators between the test and control groups:

• Number of positive cases per 1,000 catheter-days of bacterial colonization at CVC tips

• Bacterial colonization rate at the tip of other types of (percutaneous) deep vein catheters and the catheterization site (number of culture positive cases/total catheters x 100% and number of positive cases per 1,000 catheter-days), including hemodialysis, PICCO, float catheters, etc.

 Incidence rate of Central Line Associated Bloodstream Infections (CLABSI) or Catheter Related Blood Stream Infections (CRBSI)

• Type of pathogenic microorganism (G+/G-/fungal or specific species, drug-resistant bacteria, etc.) and percentage of positivity

• Securement performance of the dressing: Frequency of dressing changes associated with wearing time and warping or peeling

• Effects on the skin of the covered area, e.g. local infection, local skin irritation

3. STUDY DESIGN

3.1 Overall Design Description

This clinical trial is designed as a prospective, randomized, open-label, parallel-group controlled trial.

3.2 Study Population and Sample Size

440 subjects who meet the inclusion/exclusion criteria will be enrolled. Subjects will be adult voluntary clinical subjects, of either sex, at least 18 years of age, who are ICU patients undergoing deep venous catheterization (DVC), in which a CVC catheter must be used while other types of catheters such as hemodialysis, PICCO, and floating catheters may be used concurrently.

This study will use a positive two-sided Z test for continuity calibration and use the O'Brien-Fleming expenditure function to determine the test boundary. Assuming a baseline value of 18.7% for CVC tips colonization rate in the control group (this figure is reported by a domestic epidemiological survey) and a reduction rate of 50.0%, each group should contain at least 220 patients with CVC to reach an 80% likelihood at 5% significance level. A total of 440 valid cases are required in both groups combined. An interim analysis is scheduled for this study and will be conducted after completion of follow-up visits of 220 subjects to correct for the pre-defined sample size.

3.3 Randomization

After investigators confirm checks of inclusion and exclusion criteria, eligible participants were given a randomization number through the online randomization service system and randomly assigned to either the trial or control group to receive trial treatment in a 1:1 grouping ratio. The random number table was generated by a biostatistician using a program prior to enrollment of the first participant and then imported into the online randomization service system. See the randomization scheme for details.

3.4 Study Duration

The duration of the study is expected to be 15 months, from enrollment of the first subject to departure of the last subject.

Depending on the subject's disease treatment schedule, each study subject would be treated with the same deep vein placement for essentially no more than 2 weeks, so their participation in the study would last for approximately 3-14 days.

Process	Screening	Dressing	Treatment	Withdrawal or
	and	change visits	end	discontinuance
	enrollment		Visit	of visits
	Day 0			
Informed consent form	Х			
Assessment of	Х			
inclusion/exclusion criteria				
Randomization	Х			
Demographic	Х			
Previous medical history	Х			
Vital signs	Х		Х	Х
Blood routine test	Х		Х	Х
Record of deep vein	Х		Х	Х
catheterization				
Skin assessment around the	Х	Х	Х	Х
catheter site				
Dressing application or	Х	Х		
change (multiple times)				
Documentation of relevant	Х	Х	Х	Х
concomitant medication				
Evaluation of subject product		Х	Х	Х
(dressing edge curling, etc.)				
Total duration of			Х	
catheterization				
Total duration of test/control			Х	
dressing use				
Catheter-tip bacterial culture			Х	
Bacterial culture from skin			Х	
samples around the insertion				
site				
Blood bacteriological culture			Х	
AE/SAE	Х	Х	Х	Х
Device Defect	Х	Х	Х	Х

Table 3.1 Schedule of events

4. EVALUATION INDICATORS

4.1 Efficacy evaluation indicators

4.1.1 Major efficacy indictors

(1) Occurrence rate of bacterial colonization of the CVC tip segment and skin at the insertion site after extubation (number of culture-positive cases/total number of catheters × 100%).

The primary endpoint is the removal of the CVC from the patient with deep vein catheterization to perform catheter-tip culture and sampling and culture of bacteria from the skin around the insertion site

4.1.2 Secondary efficacy indicator

- Number of positive cases per 1,000 catheter-days of bacterial colonization at the tip of the CVC (number of culture-positive catheters/total catheter retention time (days) * 1000%));
- (2) Bacterial colonization rate at the tip of other types of (percutaneous) deep vein catheters and the catheterization site (number of culture positive cases/total catheters x 100% and number of positive cases per 1,000 catheter-days), including hemodialysis, PICCO, float catheters, etc;
- (3) Occurrence of suspected CLABSI/CRBSI, which entails catheter tip bacterial culture and blood bacterial culture
- (4) Securement performance of the dressing: Frequency of dressing changes associated with wearing time and warping or peeling

participant wear time (hours) = sum of all dressing wear times (hours) for the participant/participant dressing changes

Number, where wear time (hours) for each dressing = change date time - use date time.

Replacement due to edge lifting and droping out is defined as whenever there is a dressing replacement due to edge lifting and droping out, it is determined that the participant appears to be replaced.

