5.2 Secondary Objective(s)

The secondary objective of this study is to compare the differences in the following indicators between the test and control groups:

- Number of positive cases per 1,000 catheter-days of bacterial colonization at CVC tips
- Bacterial colonization rate at the tip of other types of (percutaneous) deep vein catheters and the catheterization site (number of culture positive cases/total catheters \times 100% and number of positive cases per 1,000 catheter-days), including hemodialysis, PICCO, float catheters, etc.

- Incidence rate of Central Line Associated Bloodstream Infections (CLABSI) or Catheter Related Blood Stream Infections (CRBSI)
- Type of pathogenic microorganism (G+/G-/fungal or specific species, drug-resistant bacteria, etc.) and percentage of positivity
- Securement performance of the dressing: Frequency of dressing changes associated with wear time and lift or drop-off
- Effects on the skin of the covered area, e.g. local infection, local skin irritation.

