2. Assessment of skin conditions around the catheter site, with reference to the standards for evaluating local skin irritation as listed in the appendix;

The following data will be collected during the follow-up visit:

1. Date and time of dressing change, site of dressing change, reason for dressing change. Scoring and assessment of edge curling in the case of dressing changes due to severely edge curling in the previous use;
2. Documentation of skin conditions around the catheter site, including erythema, edema, rash, etc., and scoring with reference to the standards for evaluating local skin irritation as listed in the appendix.
3. Any changes in medication use relevant to the trial, including mainly fat emulsions, heparin, blood transfusions and antimicrobial drugs;
4. Adverse events, device defects, complaints.

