19.4 Statistical Analyses

For patient baseline characteristics and demographic data, quantitative data will be analyzed based on t-test or rank sum test, and qualitative information will be analyzed based on Chi-square test or Fisher's exact test. CVC tip bacterial colonization rates, PICCO/hemodialysis catheter bacterial colonization rates, catheter-related bloodstream infection rates, and microbial species analysis will be analyzed by chi-square test or Fisher's exact test. Other results collected in this study, such as wearing duration, frequency of replacement, skin condition, and number of deaths, will be analyzed using t-tests or rank sum tests accordingly. The O'Brien-Fleming expenditure function will be used twice in succession to determine the test boundaries.

In addition, descriptive summaries of effectiveness and safety evaluation indicators will be presented for the entire trial and for subjects in each group. For continuous data, the data will be summarized by number of subjects, mean, standard deviation (SD), median, minimum and maximum values. For categorical data, they will be summarized by frequency and corresponding percentage.

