The number of cases, case times and occurrence rate of suspected CLABSI/CRBSI occurred in the two groups of different bacteriological culture specimens types and at catheter locations were calculated, and the two groups were compared using the chi-square test or Fisher's exact test.

The number of cases, case times and occurrence rate of positive occurrences in the two groups of different bacteriological culture specimens types were summarized by bacterial classification, specific bacterial name, and the two groups were compared using the chi-square test or Fisher's exact test, respectively.

Quantitative descriptive statistics (number of cases, mean, standard deviation, median, minimum, maximum) were used to describe the duration of dressing wear in both groups and t-test or rank sum test was used to compare the two groups. The frequency of dressing changes due to edge lifting and droping out was described for both groups of participants and the two groups were compared using the chi-square test or Fisher's exact test.

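### Dressing changes for lift or drop-off are reduced to ever/never per participant, which drops repeat failures and ignores dressing-time at risk

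*SAP*

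**What the plan says.** Protocol 5.2 lists among the secondary objectives "Securement performance of the dressing: Frequency of dressing changes associated with wear time and lift or drop-off". SAP 2.2 repeats it in nearly the same words: "Frequency of dressing changes associated with wearing time and warping or peeling".

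SAP 4.1.2 then supplies the working definition: "whenever there is a dressing replacement due to edge lifting and droping out, it is determined that the participant appears to be replaced". The English is rough, but the rule assigns a status to the participant, and one qualifying change is enough to set it.

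For the analysis, SAP 6.3.2 states that "The frequency of dressing changes due to edge lifting and droping out was described for both groups of participants" and prescribes a chi-square or Fisher's exact test.

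Protocol 19.4 places replacement frequency in a different class of methods. Results "such as wearing duration, frequency of replacement, skin condition, and number of deaths, will be analyzed using t-tests or rank sum tests accordingly".

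Three other provisions bear on the point:
- SAP 4.1.2 defines a participant's wear time as total wear hours divided by the number of dressing changes. SAP 6.3.2 compares it by t-test or rank sum test.
- SAP 6.2.3.1 summarises total dressing-use time by group, descriptively.
- Protocol 10.2.3 collects the date, time, site and reason of each dressing change. Protocol 10.2.4 collects total duration of dressing use.

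**The concern.** A frequency is a count over an amount of exposure. An ever/never status keeps only whether the count is above zero. Two things are lost.

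First, a participant whose dressing failed several times is scored the same as one whose dressing failed once.

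Second, the chance of being scored as replaced rises with dressing-time at risk. That time varies with stay (about 3 to 14 days, SAP 3.4) and with the number of catheters, because Protocol 10.2.2 has all deep venous catheter sites dressed at enrolment. The resulting proportion describes the dressing and the length of exposure together.

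At stake is the interpretability and efficiency of one component of a secondary indicator. A sponsor or reader who wants to know how much more often one dressing lifts than the other would not get that figure from the planned analysis.

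**Working it through.** The documents state no rate, effect size or power for this endpoint, so there is no planned figure to reproduce. The check sets the passages side by side and then illustrates the consequence.

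**Objective against measure**

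| Place | Quantity | Method implied or stated |
|---|---|---|
| Protocol 5.2, SAP 2.2 | Frequency of changes | None stated |
| Protocol 19.4 | Frequency of replacement | t-test or rank sum test, which suits a count |
| SAP 4.1.2 | Participant ever had a lift or drop-off change | Yes/no status |
| SAP 6.3.2 | Described by participant | Chi-square or Fisher's exact test |

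No offset, person-time or time-to-event method enters the lift or drop-off comparison. Yet the same SAP 4.1.2 expresses colonization per 1,000 catheter-days, so exposure adjustment is already accepted elsewhere in the plan.

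**Inputs for the illustration**
- Time at risk t: 3, 7 and 14 days. SAP 3.4 gives the 3 and 14; Protocol 10.2.3 gives 7 days as the expected maximum use of one dressing.
- Rate L of lift or drop-off changes per dressing-day: an assumption, 0.02 to 0.20.
- Constant rate, one dressed site. Two sites for 7 days count as 14 dressing-days.

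**Probability of being scored as replaced:** P(ever) = 1 − exp(−L·t)

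| L per day | 3 days | 7 days | 14 days |
|---|---|---|---|
| 0.02 | 5.8% | 13.1% | 24.4% |
| 0.05 | 13.9% | 29.5% | 50.3% |
| 0.10 | 25.9% | 50.3% | 75.3% |
| 0.20 | 45.1% | 75.3% | 93.9% |

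Each row is one dressing with unchanged performance. Only the exposure differs.

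**Attenuation when the true rate is halved (rate ratio 0.50):** risk ratio = [1 − exp(−L·t/2)] / [1 − exp(−L·t)]

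| L per day | 3 days | 7 days | 14 days |
|---|---|---|---|
| 0.02 | 0.507 | 0.517 | 0.535 |
| 0.05 | 0.519 | 0.544 | 0.587 |
| 0.10 | 0.537 | 0.587 | 0.668 |
| 0.20 | 0.574 | 0.668 | 0.802 |

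Worked case, L = 0.10 and t = 14: (1 − exp(−0.70)) / (1 − exp(−1.40)) = 0.503 / 0.753 = 0.668. The rate ratio is 0.50 in every cell.

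**Repeat changes discarded:** the expected count is L·t, and ever/never retains at most P(ever) of it. At L = 0.10 over 14 days, 1.40 − 0.753 = 0.647 of 1.40 expected changes per participant (46%) are not used. At L = 0.02 over 14 days, 0.28 − 0.244 = 0.036 of 0.28 (13%).

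**The case against.** The strongest reply has four parts.

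**The SAP already has a time-based securement measure.** True: wear time per change is, in effect, the inverse of the change rate. But it pools changes for every reason, including routine ones, so it does not isolate lift or drop-off.

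**Ever/never is a valid randomized comparison.** This stands. A reader might infer that two equally secure dressings would look different under the planned test. That needs dressing-time to diverge between arms after randomization, and the documents do not show that it would: allocation is 1:1, and stay is said to follow the disease treatment schedule. Chance alone is an unlikely source of a large gap. Even the largest standard deviation that a 3 to 14 day range allows, (14 − 3)/2 = 5.5 days, gives a standard error of 5.5 × √(2/220) = 0.52 days for the difference in means, so a 2-day gap would be 2/0.52, about 3.8 standard errors. Because the trial is open-label and catheter removal comes after randomization, divergence is possible, but it is not established.

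**Repeat failures may be few.** This also stands at low rates. For one site at 3% per day over 6 to 8 days, the Poisson chance of two or more changes is about 1.4% to 2.5%; at 5% per day it is about 3.7% to 6.2%. Higher rates, longer stays and several sites raise it.

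**Lift is scored as well.** A reader of Protocol 10.2.3 alone, which asks for "Scoring and assessment of edge curling in the case of dressing changes due to severely edge curling in the previous use", might conclude that lift is recorded only after severe curling. Protocol 10.2.4 and the schedules of events (Protocol 10.3, SAP 3.4) also place securement or edge-curling evaluation at the dressing-change, end-of-treatment and withdrawal visits. The SAP, however, specifies no analysis of the lift score, so those data do not fill the gap.

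Protocol 19.7 also lets methods change if the SAP documents it. SAP 9 does not mention this change. Protocol 19.4 does not limit replacement frequency to any one reason, so the departure from it is a point to reconcile rather than a clear breach.

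**Conclusion.** The concern holds as a mismatch between objective and measure. The plan sets out to compare how often dressings are changed for lift or drop-off and then tests whether each participant ever had such a change. Repeat events are discarded, and the contrast weakens as exposure grows: for a true rate ratio of 0.50 at an assumed 0.10 per day, the risk ratio moves from 0.54 at 3 days to 0.67 at 14. At 0.02 per day the movement is small (0.507 to 0.535), so the size depends on a failure rate that the documents do not give.

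The documents do not support the stronger conclusion that the planned comparison is biased between arms. The point concerns one part of a secondary indicator with no power statement; it does not touch the sample size or the primary analysis. It is a worthwhile, low-cost improvement.

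**What to change.** - **SAP 4.1.2:** define securement failure as the number of dressing changes for lift or drop-off divided by dressing-days, summed over all study-dressed sites and including time under the final dressing.
- **SAP 6.3.2:** compare arms by Poisson or negative binomial regression with log dressing-days as offset, using one record per participant, or site-level records with robust errors by participant. Report the rate ratio with its confidence interval.
- **Ever/never:** keep it as a descriptive row.
- **Protocol 19.4:** reconcile the method, and note the change in the SAP as Protocol 19.7 provides.

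The inputs are already planned: date, time, site and reason of each change (Protocol 10.2.3) and total dressing duration (Protocol 10.2.4). The case report form is not among the documents, so confirm that first application and final removal times are captured for each site. The cost is a wording change and one extra model on a secondary endpoint.

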4.2 Safety indicators

- (1) Adverse events;
- (2) Vital signs: Including temperature, respiration, pulse, systolic blood pressure, diastolic blood pressure, and study time point: Screening and enrollment, withdrawal/discontinuation of visits or end-of-treatment visits.
- (3) Laboratory Check: Blood routine includes red blood cell count, white blood cell count, platelet count, neutrophil %, neutrophil count, lymphocyte %, lymphocyte count, hemoglobin, C-reactive protein, and study time point: Screening and enrollment, withdrawal/discontinuation of visits or end-of-treatment visits.
- (4) Effects on the skin of the covered area, e.g. local infection, local skin irritation

5. STATISTICAL ANALYSIS DATASETS

5.1 Full Analysis Set (FAS)

The set of subjects determined according to the principle of Intention To Treat (ITT) refers to the data set composed by all subjects who are involved in the trial randomly and have used the trial product. The missing data were carried forward using the strategy of

WCCF (Worst Case Care Forward) in case the primary efficacy endpoints of the patients were not observed.

FAS is the primary analytical data set for evaluating validity. In addition, FAS will be used for drop-out analysis, and equilibrium analysis of basic index.

5.2 Per-Protocol Set (PPS)

PPS is a subset of the FAS and includes subjects randomly assigned to treatment with a test or control device who have not experienced significant protocol deviations. The PPS is the secondary analytical data set for evaluating validity.

5.3 Safety Set (SS)

This includes all subjects who have been formally enrolled and completed catheterization and dressing securement with the catheter in place for more than 24 hours.

This data set is used to evaluate the safety of this trial.

6. STATISTICAL ANALYSIS METHODS

6.1 General Principles

Statistical analyses will be performed using SAS 9.4.

In accordance with the O'Brien-Fleming expenditure function, all statistical tests in the final analysis were two-sided, and a p-value of less than 0.048 would be considered statistically significant for the difference being tested (except where specially described).

The description of quantitative indicators will calculate the number of cases (missing), mean, standard deviation, median, minimum, and maximum. The minimum and maximum values will have the same decimal digits retained as the raw data, but the mean, standard deviation, and median will have one more decimal digits than the raw data. However, generally the maximum number of raw data will not exceed four decimals.

The description of qualitative indicators will use the number of cases and percentages of each category. Calculation of percentage was based on non-missing data in the analysis set. Percentage was rounded to one decimal number. Unless special instruction, percentages will be calculated using the number of people in the corresponding group for each population as the denominator.

All numerically derived variables will keep two decimals, unless otherwise specified.

The treatment of missing data will be described in a separate section, otherwise all missing data will not be filled.

Missing days in the date will be filled using 1 day, and missing months will be filled using 1 month, as a general principle for filling missing dates, unless special instruction.

Baseline will be defined as the last test value prior to treatment.

Change relative to baseline in this paper will be defined as post-treatment minus baseline.

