19.0 STATISTICAL CONSIDERATIONS

This is a prospective, randomized, open-label, parallel-group controlled, single-center study designed to explore whether the subject product effectively reduces bacterial colonization in comparison with the control product. Subjects will be divided into two groups based on the random number table.

For continuous data, descriptive statistics will include the number of subjects, mean, standard deviation, median, minimum and maximum values. For categorical data, descriptive summaries will be made by frequency and percentage. Unless otherwise specified, a two-sided test will be used for all statistical tests, and a p-value of less than 0.05 will be considered statistically significant for the difference being tested.

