6.3.2 Secondary Efficacy Evaluation

- (1) Evaluation Indicators
 - Number of positive cases per 1,000 catheter-days of bacterial colonization at CVC tips;
 - 2) Bacterial colonization rate at the tip of other types of (percutaneous) deep vein

catheters and the catheterization site (number of culture positive cases/total catheters x 100% and number of positive cases per 1,000 catheter-days), including hemodialysis, PICCO, float catheters, etc;

- 3) Occurrence of suspected CLABSI/CRBSI, which entails catheter tip bacterial culture and blood bacterial culture
- 4) Securement performance of the dressing: Frequency of dressing changes associated with wearing time and warping or peeling
- (2) Evaluation method

FAS and PPS were used for evaluation.

Quantitative descriptive statistics (number of cases, mean, standard deviation, median, minimum, maximum) were used to describe the number of positive cases per 1,000 catheter-days occurring in the two groups of CVC tip bacterial colonization, and t-test or rank sum test was used to compare the two groups. In addition, a mixed linear model was developed to evaluate the difference in the number of positive cases per 1,000 catheter days of bacterial colonization between the two groups, using the number of positive cases per 1,000 catheter days of bacterial colonization of the CVC tip segment after extubation as the dependent variable, group as a fixed effect, and insertion site, skin infection of baseline at the insertion site, and their interaction as random effects.

The number and percentage of cases of bacterial colonization at the tip of other types of (percutaneous) deep vein catheters and the catheterization site after extubation were described separately for both groups with the total number of catheters and at the participant level, and the two groups were compared using the chi-square test or Fisher's exact test.

Quantitative descriptive statistics (number of cases, mean, standard deviation, median, minimum, maximum) were used to describe the number of positive cases per 1,000 catheter days occurring at the tip of other types of (percutaneous) deep vein catheters and the catheterization site after extubation in both groups. If more than one catheter of the same type was placed in the same participant, it will be analyzed with the total number of catheters and participant level separately and the two groups will be compared using a t-test or Wilcoxon rank sum test.

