8. INTERIM ANALYSIS

The interim analysis will be performed when enrollment reaches 220 participants, and this interim analysis will be performed by an unblinded team (including statisticians

and programmers) to recalculate the total sample size needed to adjust this study based on the results of the primary endpoint of 220 participants already enrolled and the dropout rate. If the results of the interim analysis show that: When the difference of the primary endpoint between the two dressings, i.e., the positive rate of bacterial culture of the CVC tip segment and skin at the insertion site (either one), is greater than 50% and the p-value is less than 0.005, and with all other considerations to support the objectives and the assumptions of the study were met, the study will be discontinued early with a final statistical analysis report. Otherwise, only issue: The decision to continue as per the protocol or to increase the sample size at a later stage; meanwhile, specific analytical findings were maintained blinded until the entire study was unblinded for final analysis. If the sample size recalculated for the interim analysis was less than or equal to that specified in the protocol, the final analysis was performed when the subsequent test was conducted to the sample size specified in the protocol; if the sample size recalculated for the interim analysis exceeded that specified in the protocol, the final analysis was performed when the subsequent test was conducted to the re-estimated sample size.

In accordance with the O'Brien-Fleming expenditure function, all statistical tests for this interim analysis were two-sided, and p-values less than 0.005 were considered statistically significant for the differences tested.

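### SAP 6.1 applies one p<0.048 rule to every final-analysis test, with no hierarchy, alpha split or exploratory label for the secondary and species comparisons

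*SAP*

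**What the plan says.** SAP 6.1 sets the decision rule for the final analysis: "all statistical tests in the final analysis were two-sided, and a p-value of less than 0.048 would be considered statistically significant". The sentence leaves room for exceptions described elsewhere, but the SAP describes none. Its only other threshold is in section 8, for the interim: "p-values less than 0.005 were considered statistically significant for the differences tested". Protocol 19.0 also has one rule for all tests, at a different level: "a p-value of less than 0.05 will be considered statistically significant for the difference being tested".

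Protocol 5.2 frames the secondary objectives as comparisons: "The secondary objective of this study is to compare the differences in the following indicators between the test and control groups". SAP 6.3.2 turns them into between-arm tests, on both FAS and PPS:

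- CVC-tip positives per 1,000 catheter-days: a t or rank-sum test, plus a mixed model.
- Other deep vein catheters: tip and site colonization, as a percentage and per 1,000 catheter-days, at catheter and participant level. For the per-1,000-day measure with several catheters of one type, "it will be analyzed with the total number of catheters and participant level separately and the two groups will be compared".
- Suspected CLABSI/CRBSI, broken down by specimen type and catheter location.
- Dressing wear time, and replacement because of lifting or drop-off.
- Organisms within specimen type, "summarized by bacterial classification, specific bacterial name, and the two groups were compared using the chi-square test or Fisher's exact test".

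Neither document gives a testing order, a condition on the primary result, an alpha split, a multiplicity statement or an exploratory label for any of these.

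**The concern.** A plan that attaches the words statistically significant to every test below one threshold lets each of them support a claim by itself. The O'Brien-Fleming boundary does not help, since it controls repeated looks at one hypothesis and not the number of hypotheses. The species family is also open-ended, because its size is known only once the cultures are read.

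What is at stake is how the secondary results may be reported. If the primary comparison fails, nothing in the plan prevents one organism, one catheter type or one unit of analysis from being presented as a significant benefit in an open-label trial of the sponsor's own dressing.

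**Working it through.** **1. The plan's own threshold.** Inputs: interim p<0.005 and final p<0.048 (SAP 8 and 6.1), with the interim at 220 of 440 subjects, so information fraction 0.5. A classic two-look O'Brien-Fleming boundary with overall two-sided alpha 0.05 gives 0.0052 and 0.0480. The pair 0.005/0.048 has an overall error of 0.0499. The 0.048 is therefore right for one hypothesis tested at two looks, and its whole correction is used on the looks.

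**2. Counting the tests in SAP 6.3.2.**

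- CVC tip per 1,000 days, two methods: 2
- Other catheters, tip/site × percentage/per 1,000 days × catheter/participant: 2 × 2 × 2 = 8
- Suspected CLABSI/CRBSI: 1
- Wear time: 1
- Lift or drop-off replacement: 1

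The total is 13, before any split by catheter type, location or specimen, and before class and species tests. Collapsed to distinct outcomes there are 5: CVC tip per 1,000 days, other-catheter colonization, CLABSI/CRBSI, wear time and lift.

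**3. Chance of at least one p<0.048 when every null hypothesis is true.** For K independent tests this is 1 − (1 − 0.048)^K. With K = 5, 1 − 0.952^5 = 0.218. For K normal statistics with common correlation ρ and critical value c = 1.977, it is

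1 − ∫ φ(u) [Φ((c − √ρ·u)/√(1−ρ)) − Φ((−c − √ρ·u)/√(1−ρ))]^K du.

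ρ is an assumption, since the documents give no value.

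| K | ρ=0 | ρ=0.2 | ρ=0.5 | ρ=0.8 |
|---|---|---|---|---|
| 5, either direction | 21.8% | 21.0% | 17.6% | 12.3% |
| 13, either direction | 47.2% | 43.9% | 32.4% | 18.5% |
| 5, favouring CHG only | 11.4% | 10.7% | 8.8% | 6.1% |
| 13, favouring CHG only | 27.1% | 22.9% | 16.2% | 9.3% |

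Independence is not credible for the 13, because many repeat the same outcome. Their usable range is 18.5–43.9%.

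**4. Allowing for near-duplicates.** Assumed correlations: 0.90–0.95 between re-analyses of one outcome, 0.5–0.7 between tip and site, 0–0.3 between other colonization and infection outcomes, 0.4 between wear time and lift, and 0 between securement and the rest. All 13 tests then give 28–32%. Without the two securement tests the figure is 21–25%. A patient-level simulation gives about 27% and 19–21% respectively. It assumes 220 per arm, 30–50% of patients with another catheter, 0–10% of those with two, tip 18.7%, skin 25%, CLABSI 3% and lift 20%.

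**5. Species tests, as an illustration.** Assume 6–15 species with frequencies proportional to 1/rank, tip 14% and skin 25% positive, 220 per arm and no effect. Use chi-square where expected counts reach 5 and Fisher's test otherwise. The chance of at least one p<0.048 among species tests alone is about 26–30%.

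**The case against.** The strongest reply is that this is a post-market study of registered devices. Protocol 19.0 describes it as exploring the effect, no passage announces a secondary claim, and readers usually treat secondary p-values as supportive. FAS and PPS are ranked as primary and secondary sets, so that duplication is not wholly unordered. These points limit the weight of the concern but do not supply the missing rule. The exploring language covers the whole study, primary endpoint included, and SAP 6.1 still calls any test below 0.048 significant.

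The objections to the size of the effect largely stand:

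- Eight of the 13 tests are variants of other-catheter colonization. Protocol 10.2.4 records only the first removal when a catheter of the same type is replaced, so catheter-level and participant-level results should mostly agree.
- Wear time and lift may truly differ between two physically different dressings that have the same antimicrobial effect.
- Fisher's test is conservative for rare outcomes. At 220 per arm and event rates of 1–5%, its actual size at the 0.048 threshold is about 0.006–0.03.

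A reader might infer that an ineffective dressing has a fixed chance of about 20–32% of a significant secondary result. The documents do not support an unconditional figure, because they give neither the number of tests nor their correlation, and the count includes results favouring control. Counting all six secondary objectives also mixes families, since the SAP analyses skin effects as a safety indicator on the safety set. Nor does the SAP pronounce the secondary results significant in advance. It sets the threshold by which they are judged.

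**Conclusion.** The concern holds as a defect of wording with a real but conditional size. One 0.048 rule governs every final test, and nothing limits what a secondary, class or species result may be said to show.

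If all nulls are true, the chance of at least one p<0.048 in either direction is about 12–22% for five distinct secondary efficacy outcomes (correlation 0.8 to 0) and about 19–44% for the 13 counted tests (correlation 0.8 to 0.2). With near-duplicates modelled it is roughly 27–32%, or 19–25% without the securement outcomes. It is higher once species tests are added. About half of each figure favours the CHG dressing. All of these rest on assumed correlations or assumed event and catheter rates.

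A reader might also infer that the primary conclusion is compromised. Testing secondaries does not change the error rate of the primary comparison, so this is a change that should be made and not a threat to the main result.

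**What to change.** 1. Amend SAP 6.1 so that the 0.048 rule applies to the primary comparison only, and reconcile it with the 0.05 in Protocol 19.0.
2. Name that comparison in SAP 6.3.1. The section currently offers tip and skin, catheter and participant level, FAS and PPS, and a mixed model besides the chi-square or Fisher's test.
3. State in SAP 6.3.2 that all secondary, class and species p-values are nominal and exploratory, with no claim of statistical significance. The species tests may stay if so labelled, since comparing organisms is a stated objective.
4. If a secondary claim is wanted, pre-specify a short fixed sequence on FAS, with one test and one unit of analysis per endpoint, tested only if the named primary comparison is significant. This gate cannot operate until step 2 is done. A Bonferroni split of 0.048 would also work: five tests at 0.0096 each give 1 − 0.9904^5 = 4.7%.

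The cost is wording alone, with no new patients or data. It should be done before results by arm are available to those who choose the hierarchy. The downside is that isolated secondary p-values can no longer be called statistically significant.
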